## **Section 2.5 Consenting Procedures**

If the person is deemed eligible for the study and is still interested in participating, provide them with a copy of the Information Sheet for Research Subjects (Appendix B), the Informed Consent document (Appendix C), and the VA brochure about participating in research studies (not pictured) to follow along with while you explain the study. They may take these home with them for their records in case they need to refer to them at a later date.

First, explain the Information Sheet for Research Subjects (Appendix B). You do not need to read it word-for-word, but you should cover all major points on the document. The first 3 bullets cover reasons that they may not want to participate in the study, while the last bullet is a reason that they may want to. Give them time to read the document and answer any questions that they may have.

If they are still interested in the study, move on to the Informed Consent (Appendix C). Again, you do not need to read it word-for-word to the participant, but you should cover all sections, give them time to read it, and answer any questions that they may have.

**Note:** Be sure to get the correct spelling of the Participant's first and last name on the top of the first page of the Informed Consent as well as their date of birth and last 4 of the SS # on the bottom of the first page. You will need to transfer this information throughout the rest of the document after the patient leaves (see your example paperwork).

**Note:** Page 4 of the Informed Consent (Appendix C) has a place for the participant to initial Yes or No about us using their data in the future. One of these options must be initialed (not checked) by the participant. Answering No to this question does not prevent them from participating in the study.

Once the consent document has been discussed make sure that any remaining questions are answered. If the person still wants to participate, have them print, sign, and date our copy of the

informed consent document. Then, you will **SIGN AND DATE** the document as the person who obtained consent (this is very easy to forget).

Finally, be sure to give them the VA brochure (not pictured) about being a research participant and answer any questions about this document that they may have.

### **Section 2.6 Randomization Procedures**

To determine which group the participant will be placed into, grab one folder from each pile (Intervention and Control) and let the participant choose one. If the folder contains the MapTrek instruction packet (Appendix D), they are in the intervention group. If the folder contains the fake paperwork, they are in the control group.

Be sure to note the group assignment in the Screening Survey and mark the survey as complete.

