## Section 1.3 Project Outline

All consented participants will be provided with a Fitbit and instructed to wear it all day, every day for the next 9 weeks (The first few participants may require an additional week or two of wear as we will not begin the first MapTrek race until we have at least 5 participants enrolled in the study. They will be told this upon enrollment.). We expect the enrollment process to take anywhere from 15 to 45 minutes, depending on group assignment and participant familiarity with using Fitbits.

This, plus an exit survey (given via text message or phone, whichever the participant prefers), will be the extent of participation for the control group.

Members of the intervention group will be instructed on how to use MapTrek, our virtual walking race, and will also be given an instruction packet to refer to later. Data collected during the first week from the Fitbit will be used to compute baseline activity level. This baseline data will be used to place participants into an appropriate initial race group. Participants are placed into groups with other individuals who are active at a similar level, so that groups will be competitive.

Each virtual walking race will begin on Monday morning and end on Saturday night. Results of each race will be announced on Sundays. Depending on their performance each week, group assignment may change. Participants will compete in 8 week-long races over the course of the study.

Participants will receive 2-4 text messages per day including a daily status report and a link to view the race. They will also periodically receive challenge messages. If a participant completes a challenge, they will be awarded bonus steps to help move them along the route quicker.

To win a race, a participant must be furthest along on the route at 11:59 pm on Saturday. There is a leaderboard within MapTrek that helps participants determine their standing within each race. Participants are allowed to choose the screen name displayed on the leaderboard so that they may remain anonymous if desired.

At baseline, we will collect the following data about all participants: first and last name, last 4 of social security number (for consent documentation and to look up records in CPRS), age, sex, race,

ethnicity, marital status, height, weight, body mass index, blood pressure, zip code, current medications, and comorbidities.

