### Section 2.4 Approaching the Patient

If you believe a patient is eligible for the study based on their CPRS data and discussions with the medical staff, approach the patient to see if they are interested in learning more and to finish any screening questions. You should only approach patients upon approval from the medical staff so that you don't disrupt clinic flow. Here is an example script (feel free to say in your own words as long as the major points are covered):

*"We are conducting a study with eligible participants to see if our map-based race will encourage Veterans to take more steps per day. We will randomize the participants to 2 different groups, a control group and an intervention group. The control group will receive a Fitbit, which is a small device that is worn on your wrist that measures your movements, to wear for approximately 9 weeks. At the end of the 9 weeks, they will complete an exit survey via phone call or online.*

*The intervention group will also be given a Fitbit and asked to wear it for approximately 9 weeks, but they will also be enrolled in a map-based race. You will be notified about your progress in the race via text message and you may also receive challenges where you can earn extra steps in the race. At the end of the 9 weeks, they will also complete an exit survey that asks about their experiences with the study.*

*Is this something that you'd like to learn more about or might be interested in participating in?"*

If the person indicates that they'd like to learn more about the study or want to participate, be sure to complete any remaining fields on the Screening Survey (Appendix A).

If any of these criteria are not met, the person is ineligible for the study. Please explain the reason for their ineligibility and thank them for their time.

If all criteria are met, you should continue on with the informed consent procedures in a room that is approved by the medical staff to avoid disrupting the clinic flow.

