### **Section 2.7 Control Group Instructions**

If the participant was assigned to the control group, the following tasks need to be completed before they leave the appointment:

- 1) Give the participant the Fitbit®. Instruct them on how to keep it charged and help them put it on for the first time.
- 2) Help the participant create a Fitbit® account by having them download the Fitbit® app from their app store and follow these steps:
  - 1) Make sure their phone's Bluetooth is turned on.
  - 2) Once the app is downloaded, open the app and click 'Join Fitbit'.
  - 3) Choose 'Charge 3' as the Fitbit Tracker.
  - 4) Click 'Set Up Your Fitbit Charge 3'
  - 5) Click 'Let's Go'
  - 6) Have them scroll up or down to their current height. Click 'Next'.
  - 7) Select their gender by clicking on the appropriate picture. Click 'Next'.
  - 8) Have them scroll left or right to their current weight. Click 'Next'.
  - 9) Have them scroll left and right to input their birth date. Click 'Next'.
  - 10) Have them enter their Full Name, Email Address, and Password. They will need to agree to the Terms of Service and Privacy Policy by clicking the check mark. Let them choose if they would like to receive news and promotions from the company.
  - 11) Click 'Next' to get past the Terms of Service and Privacy Policy screen.
  - 12) Let them Meet their Charge 3 by clicking 'Next' through the tutorial page.
  - 13) You may need to plug the Charge 3 in to complete set up.
  - 14) Make sure the Charge 3 is awake and close to the phone so that they can sync.
  - 15) Once it syncs, it will ask for the 4-digit number of the Fitbit screen.
  - 16) Click 'Next' and 'Done' to get through some tutorial information.
  - 17) They will then be logged into the Fitbit app. They may have a warning that email verification is required. They can do this at a later time.
  - 18) Show them that steps, distance, calories, and minutes of exercise are tracked on the dashboard.

3) Enroll the participant in the Control Group Boomerang Study by visiting <https://vinci.cs.uiowa.edu/meditext2> . Even though they will not be using MapTrek, they need to be entered into the Boomerang Study so that we can obtain the data from their Fitbit®.

- Log in using your username and password
- Select VA FY19-20 Control from drop down menu
- Click on the Green “Enroll Patient” button in the top right corner
- Enter the participant’s phone number, click Next

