**Editing existing Record ID 1**

Event Name: **Screening**

|   |   |
|---|---|
| Record ID   | 1   |
| 1. Are you comfortable speaking and reading in English  |  Yes
 No
<small>If no, ineligible</small>             |
| 2. What is your current age?  | 
<small>Participants younger than 18 or older than 100 are ineligible.</small> |
| 3. Do you own a smartphone with text messaging and internet capabilities?   |  Yes
 No
<small>If no, ineligible</small>             |
| 4. Do you already have a Fitbit account?  |  Yes
 No   |
| 5. Are you male or female?  |  Male
 Female  |
| 6. What is your current height (in)?  |   |
| For office use only: Date height was measured/reported  |   M-D-Y                                       |
| 7. What is your current weight (lb)?  |   |
| For office use only: Date weight was measured/reported  |   M-D-Y                                       |
| Calculated BMI  |  View equation
<small>if < 25, ineligible</small>           |
| 8. If you are enrolled in the study, would you prefer your exit survey via a text message or phone call?                              |  Text message
 Phone call                                |
| For office use only: Were height/weight/BMI self-reported or from CPRS?   |  Self-reported
 CPRS                                     |
| For office use only: Is the participant eligible?   |  Yes
 No   |
| For office use only: Randomized to intervention or control?   |  Control
 Intervention                                   |
| For office use only:  |   |
| Notes:  |   |
| Expand  |   |
| Form Status  |   |
| Complete?   |                                         |
| Lock this record for this form?  |   |

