VA MapTrek- Yr 2

IRB #: 201901762

Statistical Analysis Plan

Creation Date: 6/7/2024

VA MapTrek **Statistical Analysis Plan**

We only used data from after the start of the intervention in our analysis; the baseline data was not used to estimate the model. We defined the start date of the intervention as Day 0 for all participants.

Statistical analysis was done using Bayesian mixed effects linear regression. We included fixed effects for day-of-week, days since the start of the intervention period, group indicator (Intervention Group versus Control Group), and an interaction between group and days since intervention period start. We included two random effects: random intercept and random slope by participant. The random effects were modeled using a bivariate normal distribution.

We included vague priors on all parameters. All model fixed effects had priors of $U(-\infty, +\infty)$. We imposed slightly limited priors on the standard deviation of step counts within a person and the on-diagonal values of the covariance matrix for the random effects of $U(0, 25,000)$. This upper bound of 25,000 was at 4-5x greater than the largest plausible values for these values and was set to accelerate sampling. The off-diagonal elements of the covariance matrix were given a Lewandowski, Kurowicka, and Joe prior with a shape parameter of 2. Our prior belief is that the random slope and intercept values will be correlated but we are very uncertain about the extent of that correlation. A shape parameter of two provides a weak prior in favor of correlation.

We estimated the model using Bayesian Hamiltonian Monte Carlo (HMC) simulation using Stan No-U-Turns sampler (NUTs). We ran 6 chains for 25,000 draws on each chain. We discarded the first 5,000 draws as burn-in and assumed the remaining 20,000 draws per chain reflected the posterior equilibrium. More convergence was assessed using \check{R} , effective sample size, and the Monte Carlo error relative to the total parameter error.

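### Staff take one folder from each arm's pile and the participant picks, so staff can tell the arms apart when offering them and no random sequence exists to check assignments against

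*Protocol*

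**What the plan says.** Section 2.4 of the Protocol has staff tell patients: "We will randomize the participants to 2 different groups, a control group and an intervention group". Section 2.6 is the only operational account of how this is done. Staff are to "grab one folder from each pile (Intervention and Control) and let the participant choose one". The contents then settle the arm: the MapTrek packet means intervention, and for the other folder, "If the folder contains the fake paperwork, they are in the control group". Staff enter the result in the Screening Survey (Appendix A), in the field "For office use only: Randomized to intervention or control".

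The order of the Protocol puts this step after signed consent (Section 2.5) and after screening for age, sex, height, weight and BMI (Section 2.3).

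The SAP does not mention allocation. Its fixed effects are weekday, time since the intervention began, arm, and arm by time, with a random intercept and slope per participant. It states that "the baseline data was not used to estimate the model". Section 1.3 of the Protocol nevertheless plans for such data: "Data collected during the first week from the Fitbit will be used to compute baseline activity level".

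**The concern.** Randomisation protects a comparison when the assignment depends on chance alone and this can be shown afterwards. Section 2.6 secures neither. The staff member handling the folders took each from an arm-specific pile, and no step removes that knowledge before the offer. The dummy paperwork can hide the arm only from the participant. The way the folders are held out, a cue, or a second offer could move the pick, and none of these would leave a trace. Even with no staff influence, the only source of chance is a person's choice between two objects.

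By then staff have screened the person, may have read the medical record and have held a consent discussion, so they can have formed a view of how active the person is. Section 1.3 says that the length of the enrolment visit depends partly on the arm, and Section 2.4 asks staff not to disrupt the clinic, so the arms are not neutral for the person offering the folders. Influence is therefore plausible, although the documents contain no sign of it.

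The first objective in Section 1.2 is steps per day against control. If the offer varied with the participant, the arms would differ in activity before MapTrek began, and the planned model has nothing to correct for that.

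**Working it through.** **Does the text support the claim?**

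1. *Staff knowledge.* Section 2.6 does not state it. It follows from the rule: two piles named by arm, one person taking one folder from each, and no shuffling or masking before the offer.
2. *Sequence.* No list, block, ratio, envelope number or independent custodian appears in Section 2.6. Sections 2.3 and 2.4 and Appendix A only use the word randomise or record the outcome. The consent form and information sheet were not available to check, but they would not alter the operating instruction.
3. *Concealment before enrolment.* Consent precedes the pick, and each participant faces a fresh choice of one folder per arm. Staff therefore cannot foresee an assignment when deciding whom to enrol.
4. *Route into the estimate.* Day 0 is the start of the intervention, so the group term is the difference between arms at that point. A level difference created at allocation goes into it. A random intercept describes spread between people and does not remove a systematic difference between arms. The group-by-day interaction is less directly exposed.

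**How large could the bias be?** The documents give no SD, sample size or effect size, so every input here is assumed.

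- SD: between-person SD of true daily steps, 2,000 to 4,000, central value 3,000.
- f: share of picks steered, 10% to 30%; the rest fall 50:50.
- c: correlation of the staff impression with true activity, 0.3 to 0.5.

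Let z be standardised activity. Among steered picks, those with an impression above average go to one arm and the others to the other arm. The mean of z is then +c√(2/π) in one arm and −c√(2/π) in the other. Over all picks:

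bias = 2√(2/π) × f × c × SD = 1.596 × f × c × SD

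With SD = 3,000 this is 4,787 × f × c steps/day:

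| f | Picks going with the impression, (1+f)/2 | c = 0.3 | c = 0.5 |
|---|---|---|---|
| 0 | 50:50 | 0 | 0 |
| 10% | 55:45 | 144 | 239 |
| 20% | 60:40 | 287 | 479 |
| 30% | 65:35 | 431 | 718 |

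For the other SDs, from f = 10%, c = 0.3 to f = 30%, c = 0.5:

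- SD 2,000: 96 to 479.
- SD 4,000: 191 to 957.

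The sign reverses if less active people are steered to intervention.

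**What would baseline adjustment recover?** If baseline-week steps correlate r with true level (assumed 0.7 to 0.9), adjustment removes a share of about r²: 0.49 at r = 0.7, 0.64 at 0.8 and 0.81 at 0.9. A simulation of 4,000,000 draws gave 0.49–0.50, 0.64–0.65 and 0.80–0.81. This is an idealised figure, because it assumes that knowing the arm does not change walking in the baseline week.

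**The case against.** The strongest reply is that this procedure avoids the usual failure of weak allocation. Consent is already signed, staff cannot select whom to enrol by looking ahead, and the participant chooses freely between folders that seem meant to look alike. A blind pick of that kind may be as good as a coin toss. Section 2.6 also never says that staff knew the arm of each folder when offering them; they may have been mixed in practice. All of this narrows the concern, and the points about timing and participant masking stand in full. They do not supply a safeguard: mixing is not in the written rule, and no record would show that it was done.

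A second reply is that the size rests on no trial data. That is right. The 96 to 957 range starts at 10% steering and so leaves out weaker influence. Its upper end needs a large SD, strong steering and a good staff impression together, all in one consistent direction. It shows what the design would permit, not what is likely.

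Third, baseline-week steps are recorded after the arm is revealed, so adjusting for them could remove some real effect or add bias of its own. This also stands, and it is why adjustment belongs in a sensitivity analysis. Last, arm, age, sex and BMI are recorded for each participant, so a partial balance check is possible, although it cannot prove that allocation was sound.

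**Conclusion.** The concern holds. As written, Section 2.6 lets staff know the arm of each folder they offer, and it produces no sequence against which assignments can be verified. That reading of the procedure is firm; bias is only a possibility. Bias needs staff influence that varies with the participant, and the documents do not show any. It is zero without steering. With 10% to 30% of picks steered it is about 96 to 957 steps/day in either direction, wholly on assumed inputs. It would fall mainly on the group term, because the model carries no baseline or participant covariate. This should be fixed because the remedy is cheap and would support a claim of randomisation that at present rests on an unverifiable step.

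**What to change.** **If any enrolment remains,** replace Section 2.6 with a computer-generated 1:1 sequence, with permuted blocks of varying size if wanted. Someone not involved in enrolment should prepare it, and REDCap should release each assignment only after eligibility and signed consent are recorded. Sequentially numbered, sealed, opaque envelopes made from such a list are an acceptable alternative. The cost is one REDCap set-up and a short protocol change.

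**If enrolment is complete,** as the past-tense 2024 SAP and the study name in Section 2.7 ("Select VA FY19-20 Control from drop down menu") suggest:

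1. Describe the folder pick as it was actually done, including whether folders were mixed before the offer, and report it as a limitation.
2. Tabulate by arm the number assigned, the screening items (age, sex, BMI) and baseline-week steps. The screening items precede assignment and so are the cleaner check.
3. Add to the SAP a sensitivity analysis that includes each participant's baseline-week mean steps in the model, reported beside the unadjusted result.

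The cost is a limitation statement and a small amount of analysis on data the Protocol already plans to collect. There are two drawbacks to state. The baseline week follows disclosure of the arm. Participants without usable baseline-week data would also drop out of the adjusted model unless the SAP says how they are handled.

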### **Section 2.7 Control Group Instructions**

If the participant was assigned to the control group, the following tasks need to be completed before they leave the appointment:

- 1) Give the participant the Fitbit®. Instruct them on how to keep it charged and help them put it on for the first time.
- 2) Help the participant create a Fitbit® account by having them download the Fitbit® app from their app store and follow these steps:
  - 1) Make sure their phone's Bluetooth is turned on.
  - 2) Once the app is downloaded, open the app and click 'Join Fitbit'.
  - 3) Choose 'Charge 3' as the Fitbit Tracker.
  - 4) Click 'Set Up Your Fitbit Charge 3'
  - 5) Click 'Let's Go'
  - 6) Have them scroll up or down to their current height. Click 'Next'.
  - 7) Select their gender by clicking on the appropriate picture. Click 'Next'.
  - 8) Have them scroll left or right to their current weight. Click 'Next'.
  - 9) Have them scroll left and right to input their birth date. Click 'Next'.
  - 10) Have them enter their Full Name, Email Address, and Password. They will need to agree to the Terms of Service and Privacy Policy by clicking the check mark. Let them choose if they would like to receive news and promotions from the company.
  - 11) Click 'Next' to get past the Terms of Service and Privacy Policy screen.
  - 12) Let them Meet their Charge 3 by clicking 'Next' through the tutorial page.
  - 13) You may need to plug the Charge 3 in to complete set up.
  - 14) Make sure the Charge 3 is awake and close to the phone so that they can sync.
  - 15) Once it syncs, it will ask for the 4-digit number of the Fitbit screen.
  - 16) Click 'Next' and 'Done' to get through some tutorial information.
  - 17) They will then be logged into the Fitbit app. They may have a warning that email verification is required. They can do this at a later time.
  - 18) Show them that steps, distance, calories, and minutes of exercise are tracked on the dashboard.

3) Enroll the participant in the Control Group Boomerang Study by visiting <https://vinci.cs.uiowa.edu/meditext2> . Even though they will not be using MapTrek, they need to be entered into the Boomerang Study so that we can obtain the data from their Fitbit®.

- Log in using your username and password
- Select VA FY19-20 Control from drop down menu
- Click on the Green “Enroll Patient” button in the top right corner
- Enter the participant’s phone number, click Next
- Enter the Record ID for the participant from REDCap as the subject identifier (you do not need to enter an email address, Preferred Language should be kept as English for this study)
- Select “Go to registration page” and click Submit
- You will be taken to the Fitbit® screen and asked to provide the participant’s Fitbit login information. Once they have entered their email and password, you need to select “Allow All” from the dropdown menu and click Allow. Once this is completed, their Fitbit will be synced with Boomerang
- Return to Boomerang, Click on the Patients tab, and select the Record ID for the patient you just enrolled
- Click the Green “Add Subscription” button in the top right corner
- Select “Fitbit Reminders” as the Protocol, “Today” as the start date, the Saturday date following the end of their 9 weeks of participation as the End Date, Frequency should be set to “1”, allow the participant to choose the times they will receive reminders to wear-sync their Fitbit, uncheck both “Send end message” and “Send end email to managers”, and click Submit
- From the home screen in Boomerang, make sure the subscription worked by clicking the Patients tab, selecting the patient, and clicking on the Subscriptions tab. Make sure the subscription is set up correctly

4) Have the participant put the Fitbit® on now and instruct them to continue wearing it every day until the 9 weeks are finished (unless they are bathing, swimming, or sleeping).

5) Remind them they will receive either a text message or a phone call to complete the exit survey at the end of the study.

Once these tasks have been completed, the participant is free to leave.

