## **Section 2.8 Intervention Group Instructions**

If the participant was assigned to the intervention group, the following tasks need to be completed before they leave the appointment:

1) Give the participant the Fitbit®.

2) Help the participant create a Fitbit® account by having them download the Fitbit® app from their app store and follow these steps:

- 1) Make sure their phone’s Bluetooth is turned on.
- 2) Once the app is downloaded, open the app and click ‘Join Fitbit’.

- 3) Choose 'Charge 3' as the Fitbit Tracker.
- 4) Click 'Set Up Your Fitbit Charge 3'
- 5) Click 'Let's Go'
- 6) Have them scroll up or down to their current height. Click 'Next'.
- 7) Select their gender by clicking on the appropriate picture. Click 'Next'.
- 8) Have them scroll left or right to their current weight. Click 'Next'.
- 9) Have them scroll left and right to input their birth date. Click 'Next'.
- 10) Have them enter their Full Name, Email Address, and Password. They will need to agree to the Terms of Service and Privacy Policy by clicking the check mark. Let them choose if they would like to receive news and promotions from the company.
- 11) Click 'Next' to get past the Terms of Service and Privacy Policy screen.
- 12) Let them Meet their Charge 3 by clicking 'Next' through the tutorial page.
- 13) You may need to plug the Charge 3 in to complete set up.
- 14) Make sure the Charge 3 is awake and close to the phone so that they can sync.
- 15) Once it syncs, it will ask for the 4-digit number of the Fitbit screen.
- 16) Click 'Next' and 'Done' to get through some tutorial information.
- 17) They will then be logged into the Fitbit app. They may have a warning that email verification is required. They can do this at a later time.
- 18) Show them that steps, distance, calories, and minutes of exercise are tracked on the dashboard.

- 3) Enroll the participant in MapTrek by visiting <https://vinci.cs.uiowa.edu/maptrek2/admin/>

- o Log in using your username and password
- o Basic Strategy: start at the bottom of the screen and work your way up
- o On the Home Screen, right click on the 'Change' next to Player Icons, choose 'Open link in new tab'
- o Using the 4 categories (animals, military, outdoors, other), help the participant choose an icon
- o Navigate back to MapTrek and click 'Add' next to 'Players'

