## Appendix D

The image is divided into two main sections. The left section is a teal-colored card with the white text "GET STARTED" and a white walking person icon inside a light blue teardrop marker. The right section shows a smartphone displaying a text message. The message reads: "Hi [name], respond to this message to confirm your phone number for study MapTrek: 4 Week Pilot." Below the phone is a text block: "Before the start of the 1st race, you'll get a text message asking you to confirm your phone number." At the bottom, it says "Reply 'OK' to confirm your phone number." A small number "2" is in the bottom right corner of the right section.

GET STARTED

Before the start of the 1st race, you'll get a text message asking you to confirm your phone number.

Reply "OK" to confirm your phone number.

2

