## SYNCING YOUR FITBIT:

At least once per day, open the Fitbit® app on your phone and drag the screen down. This will sync your Fitbit® to the app and advance your character along the route.

**Tip:** Turn on “all-day sync” in the Fitbit® app on your phone, this will also help keep your progress along the route current.

4

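### Charging and syncing of the outcome device are taught differently in the two arms, which could make the step record depend on arm, in a direction and by an amount the documents do not reveal

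*Protocol*

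**What the plan says.** Protocol Sections 2.7 (control) and 2.8 (intervention) are parallel checklists. Their 18 Fitbit account steps are the same, and both end with the participant putting the device on and being told to wear it for nine weeks. The first step differs. For controls it is "Give the participant the Fitbit®. Instruct them on how to keep it charged and help them put it on for the first time". For the intervention arm it is only "Give the participant the Fitbit". The one remark about power that both lists share is "You may need to plug the Charge 3 in to complete set up", which concerns set-up.

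Syncing runs the other way. The Appendix D packet, which Section 2.8 has staff go through slide by slide with intervention participants, says "At least once per day, open the Fitbit® app on your phone and drag the screen down" and adds the tip "Turn on “all-day sync” in the Fitbit® app on your phone". Section 2.7 has no matching step. It does have staff set up a reminder subscription, from the day of enrolment to the Saturday after the nine weeks, that prompts controls to wear and sync the device at times they choose.

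On duration, the sample text message in Appendix D reads "respond to this message to confirm your phone number for study MapTrek: 4 Week Pilot", while Section 1.3 says "Participants will compete in 8 week-long races over the course of the study" and Sections 1.3, 2.7 and 2.8 give nine weeks of wear.

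The SAP models daily steps with terms for group, days since start, and their interaction. It leaves baseline data out of the model. It states no rule for what counts as a valid day and no comparison of completeness between arms.

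**The concern.** The same device measures the outcome in both arms, so its set-up and upkeep should be taught identically and only MapTrek should differ. A step is counted only while the device is powered and worn, and it reaches the study only through syncing. If one arm is taught to charge and the other is taught to sync, gaps in the record may differ by arm for reasons unrelated to walking.

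Two kinds of loss matter differently. A battery that dies during the day leaves a low but present count, which reads as less walking. A day with no record at all is a missing value; if its absence is unrelated to activity, the estimate loses precision but is not shifted.

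Because the model leaves out baseline data, nothing absorbs a recording difference that is present from the start: it falls on the group term. One that grows over follow-up falls on the group-by-days term. With no completeness check by arm, the planned analysis would reveal neither.

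**Working it through.** The documents give no completeness, charging or sync rate, so there is no planned figure to reproduce. The main check is a side-by-side reading.

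| Element | Control | Intervention |
|---|---|---|
| Ongoing charging | Taught (2.7, step 1) | Not in 2.8 step 1 or any visible Appendix D slide |
| Power during set-up | Account step 13 | Same |
| Sync at pairing | Account steps 14-15 | Same |
| How to sync daily | No step | Appendix D sync slide, talked through |
| All-day sync | No step | Appendix D tip |
| Prompts to wear and sync | Scheduled reminders through the nine weeks, frequency 1 (unit not stated) | Conditional messages during races, plus 2-4 texts a day (1.3) |
| Stated length of wear | Nine weeks | Nine weeks, in the same words; the packet's sample text carries a four-week label |

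Charging is covered better for controls. Sync technique is covered better for the intervention arm. Prompts go to both arms by different mechanisms. The net direction therefore cannot be read off the text.

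**Illustration 1: truncated days (all inputs assumed).** Suppose a flat battery halves the recorded count on an extra share p of intervention days, and the true mean is m steps/day. The shift in the intervention-minus-control difference is -p × m × 0.5.

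- m = 7,000: p = 0.02 gives -70; p = 0.05 gives -175; p = 0.10 gives -350 steps/day.
- Smallest: 0.02 × 5,000 × 0.5 = 50, so -50 steps/day.
- Largest: 0.10 × 9,000 × 0.5 = 450, so -450 steps/day.

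This covers the charging channel alone, in one direction.

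**Illustration 2: missing whole days (gap assumed).** Eight race weeks are 8 × 7 = 56 days. An arm gap in completeness of 5 to 20 percentage points is 0.05 × 56 = 2.8 to 0.20 × 56 = 11.2 days per participant. If those days are left out and are unrelated to activity, the expected bias is about zero and the cost is precision.

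**The case against.** A reader might infer that following the protocol as written makes completeness depend on arm. The documents do not go that far. They contain no rate of any kind, and the differences pull in opposite directions. Controls are not left without sync support: their scheduled reminders run to the end of the nine weeks, whereas the intervention arm's wear and sync messages are conditional. Staff also carry out a sync with every participant at pairing. What controls lack is the daily how-to and the all-day-sync tip.

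The absence of charging text for the intervention arm is also less than certain. Appendix D is only partly visible (slide numbers start at 2, the leaderboard slides are reduced to numerals, and figures are missing), and the information sheet, the consent document and the control folder's paperwork are not shown. Nor do the documents say that late syncing loses data; the sync slide links syncing to moving along the route, so it is partly intervention content. These points stand, and they limit the claim to a possible effect of unknown size.

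A second tempting inference is that the four-week label would lead intervention participants to stop halfway. This is conjecture. The label sits in a sample phone-confirmation text and is not a wear instruction. The approach script gives about nine weeks for both groups, and Section 2.8 has staff repeat nine weeks directly after the packet is explained. What remains is a contradiction in participant material.

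None of this explains why the two checklists should differ on upkeep of the shared instrument, and nothing shows that the differences cancel.

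**Conclusion.** The wording difference is established as far as the visible text goes; its effect on the data is not. Upkeep teaching for the device that supplies the only modelled outcome differs by arm, and this could produce arm-dependent gaps or truncated days. Neither sign nor size can be derived. The -50 to -450 steps/day range is purely illustrative: it assumes halved counts on an extra 2% to 10% of intervention days, means of 5,000 to 9,000 steps/day, and no offsetting loss among controls. If the losses are whole days missing at random, only precision suffers.

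The point is worth acting on because correction is nearly free and the planned analysis would not show the problem. It is a low-cost improvement and does not show that the comparison is biased. The four-week label is a separate, minor correction.

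**What to change.** 1. Replace step 1 of Sections 2.7 and 2.8 with one identically worded set-up and upkeep step: show how to charge the device, show how to sync it, and turn on all-day sync on the participant's phone. Give both arms the same one-page sheet with this content.
2. Report recorded days per participant by arm, so that any difference in completeness is visible.
3. The SAP carries a 2024 date and is written in the past tense, so enrolment may be over. If it is, report recorded days by arm and disclose the difference in instructions instead; the wording change then serves only later rounds.
4. Separately, reconcile the four-week label in the Appendix D sample text with the duration stated in Sections 1.3, 2.7 and 2.8.

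Cost: about a minute more at enrolment, one handout page, a minor revision of participant materials, and one descriptive table. No added visits, staff or data collection.
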